3.6 STATISTICAL PLAN

Quantitative values will be described as mean and standard deviation in case of normal distribution, or with median and interquartile range otherwise. Qualitative variables will be described with absolute and relative frequencies. The Student's t test for normal quantitative variables and the non-parametric Mann-Whitney U test will be used to compare the two experimental groups. Pearson's chi-square test for expected frequencies above 5 and Fisher's exact test would be used to compare the distribution of qualitative variables between groups. Statistical program R [ref] will be used, applying a statistical significance level of 5%.

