2.1. PRIMARY OUTCOMES

1. Pain (Difference between preoperative and postoperative EVA (24 hours, 10-15 days after surgery, 1 month after surgery))
 - a. Analgesia intake
2. Swelling (difference with healthy limb and difference between preoperative and postoperative (24 hours, 10-15 days after surgery, 1 month after surgery))
3. Patient satisfaction (Scale 1-5 and questionnaire)

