3.3. VARIABLES

Independent variables:

These variables will be collected during the surgery and in the subsequent from patient anamnesis, clinic history and filling the Collection Data Guide Form:

- Age (years)
- Sex (male / female)
- Dominant hand (left / right / both)
- Injured hand (left / right / two)
- Fracture classification according to American Orthopaedic (AO) (16), (17)
- Number of days from injury to surgery (days)
- Preoperative pain (VAS scale (18))
- Preoperative swelling injured hand and healthy hand. The perimeter of the wrist will be measured at the height of the proximal palmar fold in cm.

Dependent variables:

These variables are the ones we want to study and will be collected during the surgery and afterwards from patient anamnesis, clinic history and filling the Collection Data Guide Form:

- Duration of admission (hours).
- Duration of surgery (minutes).
- Duration of ischemia in group B (minutes).

- Preoperative and postoperative pain (VAS scale): Pain at baseline, 24 hours post-intervention, at the visit of the first treatment 10-15 days post-intervention and pain 1 month after the intervention.
- Intraoperative pain (VAS scale): Assessable only if it has not required sedation.
- Time (minutes) of anaesthesia administration
- Time (minutes) from the end of administration to the beginning of IQ
- Need for anaesthetic reinforcement:
 - Sedations (yes/no) and reason
 - In the case of WALANT: Taking into account the reference technique used (10), if any extra doses are needed and location within the wrist
- Postoperative analgesia during admission and discharge (drugs used, dose and frequency of use)
- Postoperative swelling injured hand and healthy hand (cm).
- Stained dressing and the presence of active bleeding due to the wound within 24 hours and during the first outpatient clinic 10 or 15 days after surgery.
- Patient satisfaction during the first outpatient clinic 10 or 15 days after surgery. → Assess satisfaction (1-5) / Would you repeat the anaesthesia type? / Would you recommend the technique?
- Description of the complications of anaesthesia.
- Description of postoperative complications.
- Mobility 24 hours post-intervention, first aid and one month later. (The mobility of the fingers, intrinsic and extrinsic muscles, Kapandji exercises 1-10 and wrist mobility will be assessed by measuring flexion-extension and prone-supination with a goniometer).
- Surgeon's experience

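### Primary pain is compared as an unadjusted change from baseline; an ANCOVA on the preoperative VAS already collected would be at least as precise, bar one degree of freedom

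*Combined protocol and SAP*

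**What the plan says.** Section 2.1 gives primary pain as "Difference between preoperative and postoperative EVA (24 hours, 10-15 days after surgery, 1 month after surgery", which is a change score at each of three visits. Primary swelling is given as "difference with healthy limb and difference between preoperative and postoperative", so baseline enters one of its two comparisons, again by subtraction.

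Section 3.6 is the whole statistical plan. For quantitative outcomes it states that Student's "t test for normal quantitative variables and the non-parametric Mann-Whitney U test will be used to compare the two experimental groups". It names no regression, ANCOVA or mixed model, and no covariate.

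The covariate exists. Section 3.3 lists "Preoperative pain (VAS scale (18" and "Preoperative swelling injured hand and healthy hand" among the independent variables. The lead-in to that list says "These variables will be collected during the surgery and in the subsequent from patient anamnesis, clinic history", which does not settle when each item is recorded. Section 3.4 places the history-taking by an external observer before surgery, but does not say whether it comes before allocation. The limitations in section 3.5 concede that the number of patients could be low.

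**The concern.** Subtracting baseline is one way to use it, but it fixes the coefficient of postoperative on preoperative VAS at 1. ANCOVA estimates that coefficient from the data. Preoperative fracture pain and residual pain up to a month after fixation give no particular reason to expect a coefficient of exactly 1. When the true slope is some distance from 1, the change score carries avoidable noise, and the arm comparison has a wider interval and less power than the same patients could give.

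What is at stake is precision on a primary outcome in a trial that expects few patients. The choice is best fixed before data are seen, because adjustment chosen afterwards invites selective analysis.

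**Working it through.** **Inputs.** The plan states no sample size, SD, effect or correlation, so there is no figure of its own to reproduce. From the documents: change-score definition (2.1), unadjusted tests at the 5% level (3.6), randomisation in blocks of 10 for similar group sizes (abstract). Assumed: two-sided testing, equal arms of n = 40 or 20, pre/post correlation r from 0.3 to 0.9, and SD ratio k = SDpre/SDpost from 0.5 to 1.5.

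**Validity.** Under randomisation and no effect, change scores have the same distribution in both arms, so the planned tests hold their level. A simulation with normal data at an assumed 30 per arm (4,000 trials per setting, simulation error about 0.3 points) agrees. Null rejection was 4.7–5.5% for the t test on change, 4.5–6.0% for Mann-Whitney and 4.8–5.4% for ANCOVA.

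**Variance.** With s = SDpost, per patient:

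- Change score: s²(k² + 1 − 2rk)
- ANCOVA: s²(1 − r²)
- Difference: s²(k² − 2rk + r²) = s²(k − r)²

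The difference is never negative. It is zero only when k = r, which is when the true slope r/k equals 1. At k = 1 the ANCOVA/change ratio is (1 − r²)/(2 − 2r) = (1 + r)/2, that is 0.65, 0.75, 0.85 and 0.95 for r = 0.3, 0.5, 0.7 and 0.9.

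**Charging the degree of freedom.** CI-width ratio = √[variance ratio × (1 + 1/(2n − 4))] × t(2n − 3)/t(2n − 2).

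- At n = 40 the penalty is √(1 + 1/76) × 1.9913/1.9908 = 1.0068.
- At n = 20 it is √(1 + 1/36) × 2.0262/2.0244 = 1.0147.

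So if the true slope is exactly 1, the interval is 0.7% wider at 40 per arm and 1.5% wider at 20. That is the worst case.

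Example, n = 40, k = 1, r = 0.5: √0.75 × 1.0068 = 0.872, or 12.8% narrower.

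**CI for ANCOVA against change score, 40 per arm (% narrower; negative = wider):**

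| k | r = 0.3 | r = 0.5 | r = 0.7 | r = 0.9 |
|---|---|---|---|---|
| 0.5 | 1.5 | −0.7 | 3.1 | 25.8 |
| 0.75 | 8.9 | 3.3 | −0.4 | 4.8 |
| 1 | 18.8 | 12.8 | 7.2 | 1.9 |
| 1.25 | 28.7 | 23.9 | 20.2 | 21.5 |
| 1.5 | 37.4 | 34.1 | 33.0 | 40.8 |

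ANCOVA is wider in two of the 20 cells. In one the slope is exactly 1 (0.5/0.5). In the other it is 0.7/0.75 = 0.93, too near 1 for the variance gain to pay for the degree of freedom. At 20 per arm and k = 1 the row is 18.2, 12.1, 6.4 and 1.1.

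**If raw postoperative VAS were tested instead.** The variance is then s², and the ANCOVA ratio is 1 − r² whatever k is. At 40 per arm the interval is 4%, 13%, 28% and 56% narrower for r = 0.3, 0.5, 0.7 and 0.9.

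**Swelling.** Girth also reflects stable body size, so r is probably high. For assumed r = 0.8 to 0.95 and k = 1, the interval is 4.5% to 0.6% narrower at 40 per arm, and 3.7% narrower to 0.2% wider at 20.

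**The case against.** The strongest case against has four parts.

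- **The test is valid and the gain is unknown.** Both are true. The interval could be a fraction of a percent wider if the slope is close to 1. What remains is lopsided: a loss of at most 0.7% (40 per arm) or 1.5% (20 per arm) against a possible gain of tens of percent.
- **The plan may not test the change at all.** The abstract names preoperative and postoperative pain, section 3.3 lists pain at each time point as a dependent variable, and section 3.6 does not say which quantity is tested. This stands in part: at low r the gain over raw postoperative VAS is much smaller than over the change (4% against 19% at r = 0.3, equal SDs). It does not rescue the plan, because ANCOVA improves on the raw comparison too over the assumed range of r.
- **The remedy is not wholly free.** Section 3.3 does not fix when the preoperative VAS is recorded relative to allocation, and a mixed model with baseline-by-visit terms estimates three baseline slopes, not one. Both stand, and both are met by wording.
- **VAS may be skewed.** Keeping Mann-Whitney as a sensitivity analysis answers this.

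Three stronger readings are tempting and not supported. A reader might infer that the planned analysis is biased or inflates type I error; randomisation rules that out.

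A reader might infer that the Mann-Whitney branch is itself the weak link. In one assumed scenario with many zero scores (40 per arm, r = 0.3), power was 33% for Mann-Whitney on the change and 34% for a t test on the same change, against 57% for ANCOVA. That gap comes from the change score and the assumed floor.

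A reader might also want "Fracture classification according to American Orthopaedic (AO" as a covariate, since section 3.5 links fracture complexity to pain. But the exclusions in 3.2 already narrow the case mix and 3.3 does not fix classification before allocation. An uninformative AO type added to baseline would leave the interval 2% wider than the change score at 20 per arm with r = 0.9.

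**Conclusion.** The point holds as one of efficiency, mainly for pain. The plan collects the baseline and uses it only by subtraction, where an estimated slope is at least as efficient before its degree of freedom is charged. The size cannot be fixed from the documents: with r, SD ratio and n all assumed, the range at 40 per arm is 0.7% wider to 41% narrower. The equal-SD figures are one row of that range, and a reader should not take them as the expected gain. For swelling the gain is small and may be nil. Nothing in the plan is invalid, so this is a free improvement and not a correction of an error.

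**What to change.** In section 3.6, make the primary pain analysis an ANCOVA at each visit, with arm and preoperative VAS as covariates. The outcome may be postoperative VAS or its change: the arm effect is identical, so the definition in 2.1 is kept. An equivalent mixed model with visit-by-arm and baseline-by-visit terms will also serve; say that it estimates one baseline slope per visit. State in 3.3 or 3.4 that the preoperative VAS is recorded before allocation. Keep Mann-Whitney on the change as a sensitivity analysis.

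Optionally, adjust each swelling outcome for its own preoperative value: injured-wrist girth for the pre/post outcome, and the preoperative injured-minus-healthy difference for the healthy-limb outcome. The latter applies only to patients with a healthy limb, since 3.3 allows "Injured hand (left / right / two". Claim little or no gain there.

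The cost is a few sentences, slightly more analysis work and, for the visit-wise ANCOVA, one degree of freedom (at most 0.7% of CI width at 40 per arm, 1.5% at 20). Which visit is primary is a separate matter that this change does not settle.

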Is WALANT Applicable in Distal Radius Fracture Osteosynthesis?

Study Protocol and Statistical Analysis Plan

October 2020

NCT (still not available)

ABSTRACT

Title → Is WALANT Applicable in Distal Radius Fracture Osteosynthesis?

Aims → To evaluate is Wide Awake Local Anaesthesia No Tourniquet (WALANT) is applicable to distal radius fracture (DRF) osteosynthesis and possible benefits of not using the ischemia cuff in distal radius osteosynthesis, by using the WALANT anaesthetic technique and compare it with patients who have undergone the current anaesthesia method (locoregional anaesthesia with or without sedation)

Material and methods → Randomized controlled study comparing patients operated on for distal radius fracture with osteosynthesis during a year (December 2020 to December 2021). The randomization will be done by 10 block in order to ensure similar numbers of patients in both groups of intervention. In the group A patients will be operated on with local anaesthesia (lidocaïne + adrenaline + bicarbonate) with or without sedation without the use of ischemia, while in group B patients will be given anaesthesia by proximal locoregional blockade with or without sedation and ischemia cuff. Immediate short-term results will be compared between both groups. Primary outcomes will be preoperative and postoperative pain, pre and postoperative swelling, and patient and surgeon satisfaction.

Results →

Conclusion →

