2.2. SECONDARY OUTCOMES

1. Evolution of the surgical wound (active bleeding and dressing condition at 24 hours and 10-15 days after surgery)
2. Postoperative mobility
 - a. Thumb mobility and opposition (Kapandji scale)
 - b. Finger mobility (capability of the patient to arrive at proximal and distal palm crease)
 - c. Wrist mobility (flexion, extension, pronation, supination, ulnar deviation, radial deviation)
3. Surgeon's technical difficulty.
 - a. Scale 1-5 (1 easy- 5 difficult)
 - b. Intraoperative stress /yes/no) and reason
4. Insufficient anaesthesia
 - a. Need of change to General Anaesthesia
 - b. Need of adding more anaesthesia
 - i. Type of anaesthesia used (sedation, local anaesthesia reinforcement, etc.)

- ii. Reason for change
- 5. Postoperative complications (total number and description)

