 - a. Technical difficulty due to lack of visualization in the surgical field (Scale 1-5. 1 no difficulties, 5 very difficult))
 - b. Added stress to the surgery (yes/no) and reason.

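### Three primary outcomes, each measured several ways, share one 5% level with no lead contrast, test order, adjustment or success rule

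*Combined protocol and SAP*

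**What the plan says.** All references are to the combined protocol and SAP.

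- **Section 2.1** numbers three primary outcomes. Pain is the change in the visual analogue score from before surgery to 24 hours, 10-15 days and 1 month, with analgesia intake listed beneath it. Swelling is given as "difference with healthy limb and difference between preoperative and postoperative (24 hours, 10-15 days after surgery, 1 month after surgery". The third is "Patient satisfaction (Scale 1-5 and questionnaire".
- **Section 3.3** fills in the questionnaire. Beside the 1-5 score it has two questions: "Would you repeat the anaesthesia type? / Would you recommend the technique".
- **Section 3.6** is the whole statistical plan. It gives descriptive summaries and two-group tests (for quantitative variables, Student's t, and "Mann-Whitney U test will be used to compare the two experimental groups"; chi-square or Fisher's test for the rest). Its only statement on error is "applying a statistical significance level of 5" percent. It does not say whether tests are one- or two-sided.
- **The Introduction's hypothesis** joins reduced swelling and reduced pain in the immediate postoperative period, with satisfaction not compromised. It names no contrast or time for either and is not turned into a decision rule anywhere.
- **The abstract** gives a different list: "Primary outcomes will be preoperative and postoperative pain, pre and postoperative swelling, and patient and surgeon satisfaction". Section 2.1 has no surgeon outcome. Section 2.2 makes surgeon difficulty secondary ("Scale 1-5 (1 easy- 5 difficult"), together with stress. Section 3.3 collects only those two, the first as "Technical difficulty due to lack of visualization in the surgical field".

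**The concern.** A 5% level per test is the error rate of a conclusion only when the conclusion rests on one test, or when a stated rule ties several tests together. Here there are several primary results and no rule. Two ways of reading the results remain open, and each has a cost:

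- **Any single significant primary result is reported as a met primary outcome.** The chance of a false claim then grows with the number of tests.
- **Pain and swelling must both improve, as the hypothesis suggests.** Testing each at 5% is then sound, but only if one contrast and one time are fixed for each. With three pain times and up to six swelling contrasts to choose from, they are not fixed.

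At stake is whether a positive report from this trial carries the stated error rate. A smaller matter is that the reader cannot tell whether the surgeon outcome is primary or secondary.

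**Working it through.** The plan states no familywise error, sample size or power, so there is no figure of its own to reproduce. The inputs are the outcome list (2.1 and 3.3) and the 5% level (3.6). Two-sided tests, exact 5% size and the correlations below are assumptions.

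**Step 1. Count the primary comparisons.**
- One test per numbered outcome: 1 + 1 + 1 = 3.
- Swelling contrasts and satisfaction items merged, analgesia not tested separately: 3 (pain) + 3 (swelling) + 1 (satisfaction) = 7. Testing analgesia as well gives 8.
- Full split: pain 3 + analgesia 1 + swelling 2 × 3 = 6 + satisfaction 3, total 13.

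**Step 2. Any one p<0.05 counts, no true effect, independent tests.** The chance of at least one false positive is 1 − 0.95^k:
- k = 3: 1 − 0.95^3 = 14.3%
- k = 7: 1 − 0.95^7 = 30.2%
- k = 8: 1 − 0.95^8 = 33.7%
- k = 13: 1 − 0.95^13 = 48.7%

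**Step 3. The same with correlated tests.** Multivariate-normal simulation, 400,000 draws, analgesia grouped with pain. Columns give the assumed correlation within / between outcomes.

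| Tests | 0.3 / 0 | 0.5 / 0.1 | 0.8 / 0.2 | 0.8 / 0.5 | 0.9 / 0.5 |
|---|---|---|---|---|---|
| 3 | 14% | 14% | 14% | 12% | 12% |
| 7 | 29% | 27% | 22% | 20% | 18% |
| 13 | 46% | 41% | 30% | 27% | 22% |

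Together with step 2 the ranges are 12-14%, 18-30% and 22-49%. Counting only false positives that favour WALANT, the independent figures 1 − 0.975^k are 7.3%, 16.2% and 28.0%, against 2.5% for a single test.

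**Step 4. Joint reading.** Suppose one of the two effects is real and certain to be detected, and the other is absent. A false joint claim then needs only one false positive, favouring WALANT, on the absent effect. With correlation 0.3 to 0.8 within an outcome:
- no pain effect, any of 3 times: 6.8% down to 4.9%;
- no swelling effect, any of 6 contrasts: 12.2% down to 6.9%.

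With one named contrast each, the figure is 5% / 2 = 2.5%.

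**Step 5. Power cost of control.** Assume a 0.5 SD difference on each endpoint and 63 per arm. The expected z is 0.5 × √(63/2) = 2.806.
- One test at 5%: Φ(2.806 − 1.960) = 80%.
- First Holm step with two endpoints (2.5%): Φ(2.806 − 2.241) = 71%.
- First Holm step with three endpoints (0.05/3 = 1.67%): Φ(2.806 − 2.394) = 66%.

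Later Holm steps recover part of the loss. By simulation at correlation 0 to 0.5 between endpoints, power for a given endpoint is about 77-78% with Holm on two and about 74-75% with Holm on three. With Holm on two and no effect, the overall error is 4.7-4.9%.

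**The case against.** The strongest objection is that no section says one significant result is enough. The hypothesis is joint and directional, and on that reading the inflation is much smaller. Step 4 is its unfavourable case. If neither effect exists, the chance of a false joint claim is only about 0.7-1.7%, even with free choice among all pain times and swelling contrasts.

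The count of 13 can also be challenged. The times in the swelling line may attach only to the pre/post contrast. The hypothesis asks only that satisfaction is not compromised, so better satisfaction would not confirm it. The stated aim is the immediate postoperative period. If that means 24 hours, four tests remain (pain, analgesia, two swelling contrasts), giving 1 − 0.95^4 = 18.5% if independent and about 14-18% if correlated. Finally, the documents give no correlations, and measures that share a baseline may be very highly correlated. A common correlation of 0.9 across all tests, extreme between different outcomes, brings 7 to 13 tests down to 11-14%.

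What stands: these points lower the figure but do not remove the gap. Section 2.1 gives the later times and satisfaction the same primary status as the 24-hour results, and every count above exceeds 5% if any one result is enough. The joint reading is nowhere stated as a rule, and it too needs a named contrast.

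A reader might infer that the trial's false-positive rate is 49%. The documents do not support that. It needs the largest count, independent tests and a success rule the plan does not state. A reader might also infer that satisfaction must lose its primary status. It need not: the abstract and 2.1 both list it as primary, and the error can be controlled with it kept.

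**Conclusion.** The concern holds in this form: the plan has three primary outcomes in several versions each, one 5% level, and nothing that ties the results to a conclusion. The sizes in the working are conditional on how the results are read and on the assumed correlations; none is the trial's established error rate. The case rests mainly on one test per outcome (12-14%) and on seven tests (18-30%). The full split of 13 is an upper case.

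The surgeon outcome is a separate inconsistency between the abstract and section 2. It enters none of these figures and adds no weight to the error argument. Surgeon satisfaction in the abstract may be a loose label for the difficulty and stress items, but the text should say so.

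**What to change.** Before any outcome data are seen:

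1. **Name one contrast and one time for each primary outcome** in 2.1. An example is change in pain score and change in injured-limb perimeter, both from before surgery to 24 hours, and the 1-5 satisfaction score. Reading the immediate period as 24 hours is an assumption for the sponsor to confirm; it is the earliest postoperative time in 2.1.
2. **State the multiplicity rule** in 3.6: Holm across the three at an overall two-sided 5%, or a fixed order with each test at 5% and testing stopped at the first failure.
3. **State the success rule:** each outcome is claimed separately, and a reduction in both swelling and pain is claimed only if both succeed.
4. **Make the rest secondary**, with confidence intervals: the other times, the other swelling contrast, analgesia intake and the two satisfaction questions.
5. **As a consistency edit**, make the abstract agree with section 2 on the surgeon outcome.

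The sponsor may instead keep only pain and swelling as primaries. That is a choice of emphasis, not a requirement of error control.

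The cost is wording in the abstract, 2.1, 2.2 and 3.6, with no new measurements. Fewer results can be called primary and some power is lost: under the assumptions of step 5, a given endpoint falls from 80% to about 77-78% with Holm on two, or about 74-75% with Holm on three. The loss deserves attention because the plan gives no target sample size and section 3.5 (Limitations) concedes that the sample may be small.
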